patients feel better about their physical function and emotional well-being. We believe that patients will feel better about their physical function and emotional health with the Integrated Care approach over the long-term.

Study Description: Usual Care will follow all the highest standards for injury treatment. Integrated Care will include medical care and emotional support. Study Staff are trained to provide emotional support and teach patients the skills for goal setting, taking ownership of journey, establishing lifelines, mobilizing resources and reducing stressors. Questionnaires and hand grip strength will be collected at the hospital and at normal follow-up visits at weeks 2, 6 and 12 and months 6 and 12. Range of Motion will be collected starting at the 2 week follow up visit.

Study Population: Patients who come to the University of Florida Trauma Center for a serious musculoskeletal injury will be asked to participate. A total of 100 people, aged 18-85 years, who have received or will receive ≥ 1 surgical procedures for their orthopedic injuries, will be included. Any major bone fractures that impair mobility and/or participation in activities of daily living and self-care will also be included. Patients may not have a brain injury and may not be using medicines to control psychological illness.

Primary and Secondary Measures: The main study measures are the Patient-Reported Outcomes Measurement Information System (PROMIS) questionnaires of Physical Functional quality of life and Emotional Well-being. Secondary measures are functional measures (Lower Extremity Gain Scale, handgrip strength, range of motion of major joints) and psychological illness questionnaires, medical complications, rehospitalizations, and comorbid disease.

Analytic Methods: We will use specific tests to find out the differences between Usual Care and Integrated Care on our emotional well-being and functional outcome, and adjust results appropriately for missing numbers. Tests will be used to make sure that the study population represents other trauma populations. Participants will repeat all measures at outpatient follow-up visits during weeks 2, 6 and 12 and months 6 and 12.

4. Background:

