6. Research Plan:

Research Design: This is a single-blinded, randomized controlled study in which the research and care teams, including the physicians, will know which patients will receive

the integrated medical care or standard medical care.²⁸ We will execute this study under the Consolidated Standards of Reporting Trials Statement²⁸ for randomized controlled trials with the Patient Reported Outcomes extension.²⁹ There are two arms to the study, an Integrated care (ICare) arm and a Usual Care (UsCare) arm. Figure 1 (following page) provides the study flow diagram for this study. After discharge from acute care, the patient will return to the outpatient orthopaedic trauma clinic for regular follow-ups. The study team will minimize the patient burden by collecting data at the normal outpatient visits at weeks 2, 6, 12 and months six and 12. Patients will be asked for email addresses so that surveys may be emailed out, if the patient prefers. Therefore, patients may complete the surveys at home prior to their follow up visits. This will be based upon patients' preferences and resources.

Patient Sample: Patients will be recruited after admission to the University of Florida's Orthopaedic Trauma service at UF Health at Shands Hospital. The study team will determine using observation whether the patient is lucid (able to understand and recall information if medicated) at the time of approach. If not, the team will wait until the patient is able and willing to hear about this study.

Inclusion Criteria:

- Patients admitted with severe or multiple orthopedic trauma
- Aged 18-85 years
- Who have received or will receive ≥ 1 surgical procedure for their orthopedic injuries
- Any major bone fractures that impairs mobility and/or participation in activities of daily living and self-care

Exclusion Criteria:

- Aged <18 or ≥ 85 years
- Have a traumatic brain injury
- Have an inability to communicate effectively (e.g., at a level where self-report measures could be answered completely; such as medicated state or mechanically ventilated)
- Currently using psychotropic medications
- Have psychotic, suicidal or homicidal ideations.

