Randomization Process: The randomization process will be performed using a random number table and recorded separately into sealed envelopes. These envelopes will be randomly placed into patient folders. After the informed consent process, facilitator will open the randomization envelope. The patient will not know what group they have been randomized to, only the facilitator and study staff will know which group the patient is in. . .

Facilitators: The facilitators are an integral part of the study team. They have all of the proper training (IRB, HIPPA, NIH, etc.) to work with patients in health care and research settings. The Facilitators will be responsible for administering the surveys to collect the data on emotional well-being. The facilitators will also be familiarized with administering the *Transform-10* Program. The facilitators are supervised by the attending orthopaedic trauma physician ([name] or [name]), [name], and a clinical psychologist, [name]. [name], Drs. [name] and [name], and [name] will also serve as mentors for the facilitators as questions arise regarding the implementation of the *Transform-10* Program. The facilitators will make daily rounds with the trauma physician and other daily visits during the patients' hospital stay to ensure they are adhering to their treatment plan and to clarify any details about the patient's injury or treatment plan. The facilitators will serve as liaisons between the hospital staff, physician, clinic staff, and discharge planner. These individuals will be in daily communication with the study team, physician, and/or other hospital personnel to ensure patient safety and that the patients' medical questions are presented back to the attending physicians. Daily monitoring of facilitators by the attending orthopaedic trauma physician and study team will occur via morning conference prior to meeting with patients and a debriefing with the study coordinator at the conclusion of each day.

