Through the use of a centralized folder, the *Transform-10 Program* will include information regarding emotional well-being, social support, and provides opportunity for the patient to openly discuss their thoughts and concerns regarding their recovery. The steps will initially be reviewed with the patient by the Facilitator(s) on the trauma floor at the hospital as it is convenient for the patients. If the patient is alert and willing to review the steps, the facilitator will spend about 10-30 minutes with the patient depending on the patient's questions, concerns, and physical state. Not all steps will be reviewed at one time. The facilitators will be aware of the patient's state and timing of delivery of the *Transform-10 Program*. The goal is to review steps 1-7 during the patient's hospital stay and the remaining steps will be covered at follow-up visits with the physician. If steps 1-7 cannot fit into the patient's hospital stay, these steps will simply be covered at follow-up visits. If previous steps covered during the hospital stay need to be reviewed, the steps will be reiterated at follow up visits. The patient's normal clinical care usually includes a hospital stay, a 2 week follow up, 6 week follow up, 12 week follow up, 6 month, and 1 year follow up visit. Therefore, these steps will be covered over the time of their recovery and care plan. Lastly, patients within this group will receive a structured, physician-approved exercise program at follow-up visits to promote movement and strength prior to beginning supervised physical therapy. The steps of the *Transform-10 program* are shown in Table 1 below^{30-35,27,36-38}.

Table 1. Integrated Care (*Transform-10 Program*): A communication-focused program of ten key steps to personal transformation after orthopaedic trauma.

Step	Process
1. Become a survivor	Move from a mindset of being a "victim" to one of being a survivor; express feelings about trauma and move forward positively.
2. Go all out for recovery	Find things that you are grateful for and appreciate goodness in others and oneself; think of this time as an opportunity to self-improve. Make your environment safe around you while you recover.

3. Movement is life	Conscious thought about and participation in motion improves recovery; celebrate progress in any motion, no matter how small or large. Higher mobility levels are related to greater societal participation and QOL. Better function improves physical safety during recovery.

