4. Set goals for recovery	Contemplate the question, " What gives my life meaning? " Break up the rehabilitation process into small increments to make the recovery process manageable, measurable and controllable.
5. Take ownership of your journey	Seize responsibility and take charge of your recovery to achieve goals. This provides daily purpose and increases self-efficacy. Develop resilience. Draw a 'care map' for you and your recovery. Adhere to safety plans from your doctor.
6. Establish lifelines with others	Use the "buddy system". Rely on a non-family member to be an objective soundboard to help deal with possible physical and psychological setbacks.
7. Mobilize all resources	Mobilize and access free resources. Sunlight, fresh air and free outdoor activities (stage-appropriate exercise) are essential to helping the body and mind recover from trauma.
8. Rally your social support	Bring family and friends together to assist in recovery.
9. Take steps to return to normal	Keep life activity patterns (sleep, diet, exercise) and body rhythms as close to normal as possible.
10. Reduce available stressors	Replace avoidable stressors with positive thoughts and activities such as mindfulness, relaxation and imagery reduces flashbacks and stress.

Data collection and Measurements: The study team will follow a systematic process for data collection. Each patient will have a folder of electronic case report forms on the REDCap repository. Form design will follow *Good Clinical Practice* rules. Within each patient folder, there will be a study checklist. When electronic case report forms are completed, REDCap updates the status to indicate 'completion'. Data will be validated at the time of input by computerized controls that ensure the validity and quality. REDCap contains system integrity measures to guarantee the integrity of the system and to protect against data loss. On a weekly basis, all records will be reviewed by the Facilitators and the Clinical Coordinator.

Patient-Reported Outcomes. Patient-reported outcomes will be primary measures of the study. Patients are the most important source of information regarding the outcomes of interest, because this study focuses on patient perceptions of functional QOL and emotional well-being. At study entry, all patients will be asked to complete surveys with a Facilitator. The combination of proposed subjective and additional objective measures will create a complete picture of the patient experience.

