Sample Size: A sample size of 100 was determined in an *a priori* manner using G*Power software program.^{55,56} Anticipating that the study population will be younger but otherwise similarly distributed as that of Zimmerman et al.⁴² the sample size, N=100, was determined to be sufficient to have a medium effect size (Cohen's $d=0.60$, power of 0.80, and alpha of 0.05). This then translates into variable detectable mean differences depending on the outcome. For example, a 6.4 point difference in the State Trait Anxiety Index (STAI; one of the psychological measures for the study) can be detected assuming a standard deviation (SD) of 10.0; for AROM a 8.3 difference with an 12.0 SD. Linear mixed effects models will be used to analyze differences between UsCare and ICare in continuous outcomes.⁵⁷ Fixed effects will include randomized treatment group, time of measurement, baseline measurement, and covariates. An interaction term between treatment group and time will be modeled to assess how longitudinal changes in the outcomes differ between treatment groups. Subject-specific effects (random effect) will also be modelled to account for intra-individual correlation across measurement occasion. For categorical outcomes, a similar approach will be employed using generalized linear mixed models with a logit-link function (i.e. mixed-effects logistic regression). Sensitivity analyses will compare the impact of different covariance structures underlying the repeated measurements (e.g. unstructured, autoregressive,⁵⁸ and compound symmetry) on the results from the mixed-effects models.

7. Possible Discomforts and Risks:

Consent: Written informed consent will be obtained after explanation to participants about all procedures and time commitments. The team members will explain to prospective participants the purpose, methods and extent of the study. Potential participants will be asked to read the informed consent form and to ask questions.

Confidentiality: There is the potential minor risk of breach of confidentiality of information

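### The protocol says patients are blinded, but Integrated Care patients can infer their arm and they rate the primary PROMIS outcomes, so the stated blinding does not protect those outcomes from expectation effects

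*Protocol*

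**What the plan says.** **The blinding claim.** Protocol section 6, Research Design, states: "This is a single-blinded, randomized controlled study in which the research and care teams, including the physicians, will know which patients will receive" which form of care. Randomization Process adds: "The patient will not know what group they have been randomized to, only the facilitator and study staff will know which group the patient is". Staff are openly aware of the allocation, so the patient is the only party the word single-blinded can refer to.

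**The outcomes.** Section 3 (Primary and Secondary Measures) says: "The main study measures are the Patient-Reported Outcomes Measurement Information System (PROMIS) questionnaires of Physical Functional quality of life and Emotional Well-being". Section 6, Data collection and Measurements, repeats the point: "Patient-reported outcomes will be primary measures of the study".

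**What each arm experiences.** Under Study Groups, Integrated Care: "The steps will initially be reviewed with the patient by the Facilitator(s) on the trauma floor", using a folder and sessions of 10 to 30 minutes. Later steps follow at clinic visits, and an exercise programme is described for this group only. Under Usual Care, the facilitator sees the patient only on physician rounds. UsCare patients get the Transform-10 materials at the 12-month visit, with a short review after their final data collection.

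**Consent.** Section 7: "Written informed consent will be obtained after explanation to participants about all procedures and time commitments". The same paragraph says that the study's purpose and methods are explained.

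The SAP does not mention blinding. Neither document describes a blinded assessor, a check on whether blinding worked, or any handling of expectation effects in the analysis or interpretation.

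**The concern.** Patient blinding matters most when the patient supplies the outcome, as here. A patient who knows that extra, supportive attention is being given may rate function and mood more favourably out of expectation or gratitude, whether or not either has changed. That shift would run in the direction hypothesised in Aims 1 and 2.

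Research Design commits the trial to CONSORT with the patient-reported outcomes extension, so the single-blind label could pass into the report. A reader could then credit a PROMIS difference with a protection that the design does not supply.

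Two conduct features add to the exposure. The Facilitators paragraph gives the emotional well-being surveys to the same staff who know the allocation and deliver Transform-10. Study Groups places the remaining programme steps within the same early-arrival period of about an hour that is used for the questionnaires, and does not fix which comes first.

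**Working it through.** **Step 1: set the passages side by side.**

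| Feature | ICare | UsCare | Protocol source |
|---|---|---|---|
| Transform-10 | Delivered personally, step by step, with a folder | Materials at the 12-month visit; review after final data collection | Section 4; section 6, Study Groups |
| Facilitator contact in hospital | Sessions of 10-30 minutes on the steps | Physician rounds only | Section 6, Study Groups |
| Follow-up visits | Early arrival for assessments, plus remaining steps | Early arrival for assessments | Section 6, Study Groups |
| Exercise programme at follow-up | Yes | Not described | Section 6, Integrated Care |
| Sham or attention-matched programme | Not applicable | Not described | Section 6, Usual Care |

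A patient who has had the study's procedures explained at consent, and is then taken through a named ten-step programme, can work out which approach is being given. That suffices for ICare. For UsCare the inference runs the other way: the patient would have to notice that the programme has not arrived. The consent explanation makes this likely, but the documents do not establish it.

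**Step 2: plan figure to reproduce.** The plan gives no figure for this bias. The only design figure used below is N=100 (section 6, Sample Size). For d=0.60, 80% power and two-sided alpha 0.05, an exact t calculation needs 45 per arm, or 90 in all. At 50 per arm the power is 84.4%. So 100 is sufficient, as the protocol says, and the blinding point does not depend on it.

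**Step 3: illustrate the consequence.** Assumptions: 1:1 allocation (no ratio is stated), 50 analysed per arm, no true effect, one unadjusted two-sided test at 0.05, and a reporting shift of b SD in favour of ICare. The documents give no value for b, so a range is shown.

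Non-centrality = b × √(n/2) = b × √25 = 5b.

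Rejection probability (normal approximation) = Φ(5b − 1.96) + Φ(−5b − 1.96).

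- b = 0.1: Φ(−1.46) + Φ(−2.46) = 0.072 + 0.007 = 0.079
- b = 0.2: Φ(−0.96) + Φ(−2.96) = 0.1685 + 0.0015 = 0.170
- b = 0.3: Φ(−0.46) + Φ(−3.46) = 0.3228 + 0.0003 = 0.323

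The exact t-test gives 7.9%, 16.8% and 31.8%. With 45 per arm it gives 7.6%, 15.5% and 29.1%. For scale, b = 0.2 is one third of the design effect (0.2/0.60).

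**The case against.** **Blinding patients to a psychosocial programme is usually impossible, and the protocol is open about staff knowledge.** This stands. The absence of patient blinding is not the fault. The fault is claiming it and planning nothing for the consequence.

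**A reader might infer that nobody in the trial is blind.** The documents do not support that for UsCare. No passage says that patients are told their group label. UsCare patients also have an assigned facilitator and attend the same early visits, and the consent form is not available to check. Awareness in one arm is still enough to bias the comparison.

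**A reader might also infer that UsCare receives no programme content until measurement is over.** The protocol does not quite say that. The materials come at the 12-month visit, and only the review is placed after the final data collection.

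**The percentages are generic.** This also stands. They would fit any unblinded two-arm comparison of this size, and they describe a single test, whereas the plan is a mixed model with a baseline term and unspecified multiplicity corrections. Such corrections would lower the rate per test. Baseline adjustment would not remove a shift that arises after allocation is known. By reducing residual variance, it could make a given shift easier to detect.

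**Objective measures are also collected.** The Lower Extremity Gain Scale (LEGS), grip strength and range of motion are less open to self-report bias, but they are secondary and have no named blinded assessor. Only ICare is described as having the exercise programme. A genuine emotional benefit need not change these measures or readmissions. They therefore cannot decide whether a PROMIS difference is real.

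**Conclusion.** The concern holds. The patient-blinding statement cannot be reconciled with the way ICare is delivered, and the patient is both the only party said to be blinded and the source of the primary outcomes. This is firm for ICare and a reasonable but unconfirmed inference for UsCare. Any expectation effect would favour ICare.

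Its size is unknown. The figures of about 8%, 17% and 32%, against a nominal 5%, rest on assumed shifts of 0.1, 0.2 and 0.3 SD, an assumed 50 per arm, and one unadjusted test with no true effect. They show sensitivity and are not estimates of the bias in this trial. Nothing here shows that a PROMIS benefit would be spurious, only that the stated blinding could not be used to rule out an expectation effect. The change should be made: it concerns a stated design property bearing on the primary outcomes and is cheap to correct.

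**What to change.** 1. In Research Design and Randomization Process, replace the single-blind label and the statement about patient knowledge with open-label to patients and staff. State exactly what, if anything, is withheld from patients, and keep this consistent with section 7, where the purpose and procedures are explained. A claim that patients do not know the hypothesis would need the same check.
2. Describe both arms to patients neutrally, as two ways of delivering care.
3. Have patients complete the surveys themselves, by the email route that Research Design already allows or on arrival, before any Transform-10 step is reviewed at that visit. The facilitator who delivers the programme should not administer them. Align the passages that have entry surveys completed with a facilitator (Data collection and Measurements) and staff present throughout data collection (section 7, Stress).
4. Add one expectation item to the study-entry surveys, preferably before the envelope is opened; the protocol does not fix that order. Asked only at exit, the answer would be coloured by recovery. Add one perceived-group item at month 12, before the UsCare materials are handed over. Report both by arm.
5. State in the SAP that PROMIS differences will be reported as unblinded self-report in which an expectation effect cannot be excluded. Do not make corroboration by LEGS, grip or readmissions a condition for accepting a PROMIS benefit.

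**Cost:** wording changes, a reordering of tasks within existing visits, two survey items and a more cautious claim. No added visits are needed.

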to twelve months depending on the patient's clinical care plan. The UsCare group will get all of the materials that make up the *Transform-10 Program* at their 12 month follow up visit. Following their final data collection, the facilitator will briefly review the *Transform-10 Program* (ten steps) with the patient and address any questions that the patient has.

2. Integrated Care (ICare). The Integrated Care approach provides Usual Care processes plus simultaneous psychosocial support via the *Transform-10 Program*. Integrated Care was consolidated using the direct guidance of our Patient Advisory Panel, Partners and practitioners who care for trauma patients. We have identified psychosocial components and resource content to help patients focus on the positive and productive pathways necessary to cope with stress and achieve a high QOL. These key components can be adapted for different hospital settings, geographical locations and available resources when implemented in a larger scale. Content of the Integrated Care was based on patient needs, previous outcomes research and techniques advocated by our Partners. This delivery-of-care system format and the transformative skills that are taught will provide the patients the information and resources they need to help them reintegrate back into home, community and work activities. These steps may also improve quality of care and improve patient safety. Trained 'Facilitators' will be trained to administer the *Transform-10 Program*. These Facilitators have a background in related health fields such as licensed athletic trainers.

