categorical study variables and demographics (means and standard deviations for continuous variables, frequencies and percentages for categorical variables). Chi-square for frequency distributions will be used for patient satisfaction to test main effects of time and treatment and their interaction, on patient satisfaction; however, because patient satisfaction will only be measured at the end, a standard general linear model will be used. The primary analyses for all aims will utilize a mixed model repeated measures approach. These analyses can assess the main effects of treatment and time on outcomes, as well as their interaction (treatment x time). Specifically, independent variables will include care approach (integrated vs standard) and time point (admission, 2 weeks, 6 weeks, 3 weeks, month 6, and 12 months). Dependent variables will include all functional measures (actual and perceived). Mixed models are the preferred approach to analyze data with repeated measures; these models can account for correlation among repeated measurements, flexible time effects, and can handle missing data. Significant interactions between treatment and time would indicate that the change in the outcomes (i.e. slope) was dependent on the patient's treatment group. If a significant interaction is identified, the Preacher method will be used to estimate the magnitude and direction of the interaction. A p value will be established *a priori* at <0.05 for all statistical tests. Continuous data that are not normally distributed will be transformed prior to analysis. Appropriate multiple testing corrections will be performed to limit Type I error.

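### Late questionnaires are collected around clinic visits, with no step to obtain them from patients who no longer attend, so loss at months 6 and 12 may depend on recovery

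*Protocol*

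**What the plan says.** Protocol section 6, Research Design, has data collected at the normal outpatient visits at weeks 2, 6 and 12 and months 6 and 12, for all patients. It adds: "Patients will be asked for email addresses so that surveys may be emailed out, if the patient prefers". The next sentence describes this as completing the surveys at home ahead of a follow-up visit.

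Study Groups asks both arms to come in about an hour before the physician appointment for functional tests and questionnaires. The Usual Care paragraph has follow-up measures taken at typical outpatient times out "to twelve months depending on the patient's clinical care plan". It also gives Usual Care patients the Transform-10 materials at their 12-month visit. The Integrated Care paragraph says normal care usually includes visits up to one year. It aims to cover steps 1 to 7 in hospital, after which "the remaining steps will be covered at follow-up visits with the physician".

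Patient-reported outcomes are named as primary (Data collection and Measurements). On missing data, the Statistical Analysis section and the SAP say that mixed models can handle it, and the abstract promises appropriate adjustment without naming a method. The only sensitivity analysis named, under Sample Size, compares covariance structures. No visit window, attrition allowance or contact step for patients no longer seen is stated.

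**The concern.** Whether a patient still has a clinic visit at 6 or 12 months can depend on how well that patient has recovered, and recovery is what the primary questionnaires measure. If well-recovered patients stop attending and nothing else prompts a survey, the late data come disproportionately from those doing less well.

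A mixed model gives valid estimates when the missingness is explained by scores already observed. It does not do so when absence depends on the patient's current, unrecorded state. Changing the covariance structure does not test that assumption.

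Two things are at stake. One is the late between-arm comparison, if the loss is selective and differs by arm. The other is precision, because the sample size carries no stated allowance for loss. Questionnaires need no clinic visit, so much of this risk is avoidable.

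**Working it through.** **1. The plan's own sample size.** Inputs from Sample Size: "A sample size of 100 was determined in an" a priori manner, for a "medium effect size (Cohen's $d=0.60$, power of 0.80, and alpha of 0.05". Sidedness is not stated ("at <0.05 for all statistical tests"), so I take two-sided. The allocation ratio is not stated ("There are two arms to the study, an Integrated care (ICare) arm and a Usual Care (UsCare) arm"), so I take 1:1.

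n per arm = 2(1.96 + 0.842)² / 0.60² = 2 × 7.85 / 0.36 = 43.6, so 44. The t-based value is 44.6, so 45. The total is 88 to 90, not 100. With 50 per arm, power is 0.84 (t-test). The figure of 100 equals 90/(1 − 0.10), but the documents state no 10% allowance. N = 100 is therefore sufficient, with room for about 11% loss (1 − 2 × 44.6/100).

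**2. Power if patients are lost (illustration).** Two-sample t-test at one visit, complete cases, equal loss in both arms, d = 0.60. The normal approximation is Φ(0.60·√(n/2) − 1.96). The loss rates are assumptions.

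| Analysed | Per arm | Normal | t-test |
|---|---|---|---|
| 100 | 50 | 0.85 | 0.84 |
| 90 | 45 | 0.81 | 0.80 |
| 80 | 40 | 0.765 | 0.755 |
| 70 | 35 | 0.71 | 0.70 |

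The planned model uses all visits and a baseline covariate, so these are not its power.

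**3. Bias in observed 12-month means, no true effect.** Assume a normal outcome in SD units, split at the median into doing poorly and doing well. The two half-means are ∓√(2/π) = ∓0.798. Let attendance be 0.90 among those doing poorly and *a* among those doing well. The observed arm mean is 0.798·(a − 0.90)/(a + 0.90):

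- a = 0.50: 0.798 × (−0.40/1.40) = −0.228
- a = 0.60: 0.798 × (−0.30/1.50) = −0.160
- a = 0.70: 0.798 × (−0.20/1.60) = −0.100
- a = 0.90: 0

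The bias is the Integrated Care value minus the Usual Care value:

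| Usual Care a | Integrated Care a | Bias (SD) |
|---|---|---|
| 0.60 | 0.70 | 0.06 |
| 0.50 | 0.70 | 0.13 |
| 0.60 | 0.90 | 0.16 |
| 0.50 | 0.90 | 0.23 |

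With the same *a* in both arms the bias is zero. Swapping the arms reverses the sign. For scale, the planning effect is 0.60 SD, and the standard error of a difference with 50 per arm is √(2/50) = 0.20 SD.

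**4. After adjustment for earlier visits.** I simulated the same four pairs with complete data at all earlier visits and adjusted for them by regression. For assumed between-visit correlations of 0.5 to 0.9 (compound symmetry or autoregressive), the remaining bias was about 0.01 to 0.17 SD. The documents give no correlation, so no narrower figure is justified.

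**5. Same loss rule in both arms, with a true effect.** Assume a Usual Care mean of 45, SD 10 and a true difference of 6. Let patients scoring above 45 or 50 be missing with probability 0.3, 0.5 or 0.8. The estimated difference ranged from 4.1 to 6.1 and power from 0.46 to 0.78. Marked shrinkage came only with heavy selective loss.

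**The case against.** The strongest reply is that the protocol does not leave late follow-up to chance. It schedules months 6 and 12 for everyone, calls those visits usual care, and asks both arms to attend on the same terms. The care-plan phrase can be read as allowing the timing to vary, not as waiving late data. Email completion exists, so the primary questionnaires are not strictly bound to the clinic. There is also a study checklist and a weekly review of records. All of this stands, and it limits the point to a gap in how data are obtained from patients who stop attending. The scheduled dates say when data are wanted. Neither they nor the email option says how data reach the study without a visit.

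A reader might go further and infer that attendance will be higher in Integrated Care, because programme steps are delivered at visits, and so conclude that the 12-month result will favour that arm. The documents do not support this. Most steps are meant to be finished in hospital, Usual Care patients have their own reason to attend at month 12, and no attendance figures are given. Differential attendance is conjecture.

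A reader might also take the power figures as the power of the trial. They are not. The analysis is a mixed model over all visits, to which patients with partial data contribute, and no passage makes month 12 the primary time point.

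**Conclusion.** The point holds as a weakness in the collection rule, not as a demonstrated bias. As written, the plan can lose late primary data in a way related to recovery, and no planned analysis examines that possibility.

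The size and direction are unknown. Under the null there is no bias if both arms lose patients by the same rule. The 0.06 to 0.23 SD range rests on assumed attendance that differs by arm and on a median split, and applies to observed means before any adjustment. The fall in power from 0.84 to 0.80, 0.755 and 0.70 with 100, 90, 80 and 70 analysed is a single-visit illustration. A change is worth making because it is cheap and acts on the cause.

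**What to change.** Amend the protocol as follows:

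- Send the PROMIS and psychological questionnaires from REDCap to every patient in both arms at fixed dates from randomisation (weeks 2, 6 and 12; months 6 and 12), whether or not a clinic visit is booked, with a set window and a reminder.
- Remove the care-plan condition for questionnaires, and tie only grip strength, LEGS and AROM to visits.
- Add to the SAP a sensitivity analysis in which missing late scores are allowed to differ from what earlier scores predict, with the departure varied separately by arm.

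The cost is a short amendment, a REDCap schedule and some reminder work for existing staff; electronic forms and emailed surveys are already planned. The downside is a mix of home and clinic completion, so the mode should be recorded.

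Remote completion must also be reconciled with two parts of section 7: the statement that staff are present throughout data collection (Protections Against Discomforts and Risks, Stress) and the Distress Referral Protocol, which relies on survey scores and a care-team interview. How to reconcile them is for the investigators.
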